1.0 OBJECTIVES

The aims of this proposed pilot study are:

- 1.1 To determine if pre-treatment plasma levels of cytokines and/or biomarkers associated with inflammation and immune activation are elevated in persons with HL;
- 1.2 To evaluate the effect of brentuximab-containing AVD therapy on plasma levels of these biomarkers following 1 cycle of therapy, following 3 cycles of therapy, at the conclusion of therapy, and at 3, 6 and 12 months after the conclusion of therapy, to identify the clinical correlates with regard to tumor response and disease-free survival.

2.0 BACKGROUND

We have seen that elevated serum/plasma levels of several molecules associated with immune activation and inflammation, including sCD30, CXCL13, IL-6 and IL-10, occur preceding the diagnosis of AIDS-associated NHL, as well NHL, and HL in presumably immunocompetent persons⁶³⁻⁶⁶. These studies were all done using specimens obtained from several prospective longitudinal cohort studies. In a prior study in the AMC, we also assessed the effect of treatment for AIDS-associated NHL on plasma levels of these biomarkers, finding that treatment resulted in a marked decrease in many of these molecules, and that pre-treatment initiation plasma levels of CXCL13, IL-6 and IL-10 were predictive of subsequent CR to treatment⁶³⁻⁶⁶. In fact, in multivariate analysis, CXCL13 levels proved to be better predictors of subsequent clinical response that IPI or other established prognostic markers (8, 9). Therefore, biomarkers, including sCD30, IL-6 and IL-10 are known to be elevated preceding HL and NHL, and levels of these molecules may be associated with subsequent response to treatment in AIDS-NHL. However, little is known about these biomarkers in HIV infection-associated HL.

3.0 RATIONALE

HIV-driven inflammatory cytokine production has the potential to contribute to the growth of AIDS-associated cancers, including HL, and enhanced production of these and other B cell-stimulatory molecules may contribute to the genesis and/or growth of HL. Additionally, dysregulated infection with EBV may contribute to immune activation and inflammation. However, there is little information available on the effect of treatment of AIDS-associated HL with brentuximab on serum levels of these biomarkers, nor on the prognostic significance of such biomarkers.

The recent availability of multiplexed immunometric assays has made possible the simultaneous assessment of several of these immune activation and inflammation-associated factors, using small volumes ($<500 \ \mu$ l) of serum or plasma.

The results of this study will provide information on immune activation/inflammationassociated biomarker plasma levels in HIV-associated HL, and on effects of AVD-BV therapy for HL on these biomarkers, as well as on the prognostic value of such biomarkers in those receiving AVD-BV treatment.

4.0 EVALUATIONS

Plasma levels of cytokines and inflammation-associated molecules will be determined at the following study visits: pre-treatment (entry), and following 1 cycle of therapy, following 3 cycles of therapy, at the conclusion of therapy (6-8 weeks post treatment discontinuation), and at 3, 6 and 12 months after the treatment discontinuation visit.

5.0 ANALYSES

The working hypothesis that will be tested is that participants who will achieve clinical CR will have plasma levels of sCD30, IL-6 and IL-10 that fall within the normal range, following the conclusion of therapy.

Levels of cytokines and inflammation-associated biomarkers will be determined using two Luminex-based panels. The first is a high-sensitivity cytokine panel that can detect human IL-1 β , IL-2, IL-4, IL-5, IL-6, IL-8, IL-10, IL-12, TNF α , VEGF, GM-CSF, IFN γ . The second is a soluble receptor/inflammatory cytokine panel: BAFF/BLyS, sCD14, sIL-6R, sgp130, sIL-2R, sTNF-R2, CXCL13, sCD30 (or sCD27). Both of these panels are produced by R&D Systems, and have been used by us extensively in prior epidemiologic studies. The cytokine panel has yielded results that compare well to ELISA results for IL-6 and IL-10. The soluble receptor/inflammation panel yields detectable results for these biomarkers in the majority of persons tested.

2 mL of plasma in 1 mL aliquots should be sent in batch at the end of the study to the [name] laboratory.

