1.2 Secondary Objectives

- 1.2.1 To evaluate the toxicity of AVD and brentuximab vedotin with HAART.
- 1.2.2 To estimate the partial response (PR) rate, complete response (CR) rate, overall survival (OS), and event free survival (EFS) at 2 and 5 years.
- 1.2.3 To evaluate the effect of AVD and brentuximab vedotin on CD4 and CD8 counts after cycle 1, 4, at the end of therapy, and every 3 months after treatment completion for one year.
- 1.2.4 To investigate the prognostic value of FDG-PET/CT scans at baseline, after cycle 2, and at treatment completion, with respect to 2-year progression free survival.
- 1.2.5 To evaluate HAART status at baseline and to correlate this with tumor response to therapy and OS and PFS.
- 1.2.6 To characterize the histologic subtypes in HIV-HL in the highly active antiretroviral therapy (HAART) era.
- 1.2.7 To assess the neurotoxicity of HAART in combination with AVD and brentuximab vedotin.
- 1.2.8 To evaluate effect of AVD and brentuximab vedotin on viral load after cycles 1, 4, at completion of therapy, and every 3 months after treatment completion for one year.
- 1.2.9 To perform pharmacokinetic and immunogenicity studies to determine drug levels during therapy (See Section 10.0 and Appendix IX).
- 1.2.10 To perform miRNA profile analysis on the HIV-HL tumor specimens and to correlate miRNA expression with OS, PFS, tumor response to therapy, histologic subtype of HIV-HL, and HIV disease characteristics (See Section 10.0 and Appendix VIII).
- 1.2.11 To perform tissue microarray analysis on HIV-HL tumor specimens and to correlate the markers studied with OS, PFS, and tumor response to therapy (See Section 10.0 and Appendix VIII).
- 1.2.12 To identify EBV associated tumor derived DNA in the plasma of study participants, and to correlate these levels during therapy with disease response and OS (See Section 10.0 and Appendix XI). This objective will only be performed in the Phase II portion of the study.

- 1.2.13 To identify cytokines in the plasma of participants during therapy that can be used as tumor and prognostic markers. (See Section 10.0 and Appendix X). This objective will be done only in the Phase II portion of the study.
- 1.2.14 To assess latent and expressed HIV reservoirs before, during, and post chemotherapy. To understand how cytotoxic chemotherapeutic agents affect HIV expression (See Section 10.0 and Appendix XII).

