8.4 Early Discontinuation of Therapy

- 8.4.1 Participants discontinuing therapy early (i.e., PD or stable disease, administrative reasons, participant non-compliance, etc.) will have a medical history update and complete physical examination. The examination will include performance status and blood drawn for the following studies within 1 month after treatment discontinuation, unless otherwise noted. See Section 4.7 for a list of reasons for study termination. Participants will be followed for survival only for 5 years after the last date of treatment:
 - 8.4.1.1 CBC with differential.
 - 8.4.1.2 Serum chemistries: electrolytes (Na, K, Cl, bicarbonate, Ca, Mg, and phosphorus), glucose, blood urea nitrogen (BUN), creatinine, total bilirubin, alkaline phosphatase (ALP), LDH, total protein, albumin, AST and ALT.
 - 8.4.1.3 CD4 and CD8 cell count (do not repeat if done within 1 month from removal from treatment).
 - 8.4.1.4 HIV-1 RNA viral load to be assessed by any FDA-approved viral load assay (evaluated at the local laboratory, do not repeat if done within 1 month from removal from treatment).
 - 8.4.1.5 Pharmacokinetic/Immunogenicity studies in select Phase II participants only. See Section 10.1 and Appendix IX for time points and sample processing.
 - 8.4.1.6 Blood samples will be taken for analysis of latent and HIV reservoirs. See Section 10.0 and Appendix XII for time points needed, sample processing, and shipping instructions (do not repeat if done within 1 month from removal from treatment).
 - 8.4.1.7 Plasma samples to be taken for EBV tumor DNA studies. See Appendix XI for sample processing and shipping instructions. This will only be performed on the Phase II portion of the study.
 - 8.4.1.8 Plasma samples to be taken for and cytokine studies. See Appendix XI for sample processing and shipping instructions. This will only be performed on the Phase II portion of the study.

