10.0 CORRELATIVE STUDIES

For this protocol, we propose three correlative studies: miRNA analysis (see Section 10.2 and Appendix VIII), Tissue Microarray Studies (TMA) (see Appendix VIII), and Pharmacokinetic studies (PK) (see Section 10.1 and Appendix IX). We will collect either the paraffin blocks or Cores from these tissue and multiple unstained slides as a requirement for study entry to perform the miRNA and the TMA studies in addition to central pathology diagnosis confirmation. We will then correlate findings with the outcomes of participants enrolled on this trial in addition to their HIV infection characteristics. Please see Section 10.1 and Appendix IX for a detailed description of the PK studies to be performed in this clinical trial using serum isolated from participants during therapy.

In addition, upon acquisition of funding, we propose 3 more correlative studies. 1) We will analyze the Granzyme B to FoxP3 ratio on paraffin sections, to determine if these values, which have been reported to be prognostic indicators in non-HIV associated cHL, also correlate with outcome in HIV-HL⁶² (see Appendix VIII). 2) We will also screen participant's plasma for molecules associated with immune activation and inflammation. specifically sCD30, CXCL13, IL-6 and IL-10. In a prior study in the AMC, we also assessed the effect of treatment for AIDS-associated NHL on plasma levels of these biomarkers, finding that treatment resulted in a marked decrease in many of these molecules, and that pre-treatment initiation plasma levels of CXCL13, IL-6 and IL-10 were predictive of subsequent CR to treatment^{63,64}. In fact, in multivariate analysis, CXCL13 levels proved to be better predictors of subsequent clinical response that IPI or other established prognostic markers^{63,64}. We will confirm if these molecules are prognostic in HIV-HL as well as these molecules were also found to be elevated in these participants^{65,66} (see Appendix X). 3) As HIV-HL is co-infected with EBV, an attempt will be made to detect levels EBV derived tumor DNA in the plasma and use this as a tumor marker and a prognostic one. To do these last two studies, we will also collect plasma samples over time throughout therapy and post therapy to see how these biomarkers change over time (see Appendix XI).

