
To this end, as a correlative study in this clinical trial, we will analyze the miRNA profiles of the paraffin-embedded tumor samples of the study participants. This analysis will be performed using high throughput sequencing to comprehensively define the miRNA expression, as described previously. As controls, reactive lymph nodes from HIV-infected and uninfected participants, as well as non-HIV HL samples that are EBV positive will be used.

We will also correlate miRNA expression with overall survival, tumor response to therapy, histologic subtype of HIV-HL, and HIV disease characteristics to identify miRNAs that could act as prognostic and diagnostic markers.

Please see Appendix VIII for a detailed description of specimens required, sample processing, and shipping.

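### The only test in Appendix X, normal cytokines after therapy in CR participants, cannot by itself show that a marker tracks or predicts response

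*Combined protocol and SAP*

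**What the plan says.** Secondary objective 1.2.13 of the AMC protocol is "To identify cytokines in the plasma of participants during therapy that can be used as tumor and prognostic markers". Section 10.0 adds, for the same molecules, "We will confirm if these molecules are prognostic in HIV-HL".

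Appendix X, section 1.0 gives two aims. Aim 1.1 is "To determine if pre-treatment plasma levels of cytokines and/or biomarkers associated with inflammation and immune activation are elevated in persons with HL". Aim 1.2 follows levels after cycles 1 and 3, at the end of therapy and at 3, 6 and 12 months, "to identify the clinical correlates with regard to tumor response and disease-free survival".

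Appendix X, section 5.0 then states a single working hypothesis: "participants who will achieve clinical CR will have plasma levels of sCD30, IL-6 and IL-10 that fall within the normal range", after therapy. Appendix XIV, section 5.0 repeats the sentence. Neither appendix defines the normal range, and Section 11.4 contains no cytokine analysis.

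The rationale in Appendix X, section 3.0 says "HIV-driven inflammatory cytokine production has the potential to contribute to the growth of AIDS-associated cancers", so HIV is a recognised source of these molecules. No control group is named for the cytokines. The miRNA study does name one: "As controls, reactive lymph nodes from HIV-infected and uninfected participants, as well as non-HIV HL samples that are EBV positive will be used" (Section 10.2).

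**The concern.** A tumour marker should move with the tumour, and a prognostic marker should separate participants who do well from those who do not. The stated hypothesis looks only at participants already known to be in CR and asks whether they are normal at the end.

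That leaves two gaps. A participant who was normal before treatment counts as support although nothing changed. A marker that falls to normal in everyone, responder or not, also meets the hypothesis. The documents make the second case plausible. Section 10.0 reports that treatment markedly lowered many of these molecules in an earlier AIDS-NHL study. Section 2.4.3 links sCD30 to HIV viremia, while eligibility requires only 7 days of HAART before therapy.

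Aim 1.1 has a related limit. Every participant has both HIV and HL, so a raised pre-treatment value cannot be assigned to HL.

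At stake is a favourable biomarker report for a marker that may carry no information about response.

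**Working it through.** **The plan's own figure.** Appendix X gives no N, threshold or pass rule. The only sample size is the phase II 51, for 2-year PFS: n = 1.96² × 0.85 × 0.15 / 0.10² = 48.98, so 49. At 51 the half-width is 9.8 points, so the stated ±10% is met. It does not size the cytokine work.

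**N for the cytokine aim.** The LYSARC protocol, section 16.1 item 13, marks this objective as not applicable in France, where 20 of the 51 are expected: 51 − 20 = 31. AMC Appendix I, footnote V, requires cytokine studies of all participants. Both 31 and 51 are carried below.

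**CR rate.** Assumed 87%, from the cited ABVD-with-HAART study (54 of 62; Section 2.3). That gives about 27 CR and 4 non-CR of 31, or 44 and 7 of 51.

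**Uninformative marker.** Let the chance of a normal value after therapy be q in everyone. The documents give no q or pass rule; both are assumed.

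| q | N (CR) | Expected normal in CR | Chance exact 95% lower limit > 50% | Chance ≥ 80% are normal |
|---|---|---|---|---|
| 90% | 31 (27) | 24.3 | 99.6% | 95% |
| 80% | 31 (27) | 21.6 | 84% | 54% |
| 90% | 51 (44) | 39.6 | > 99.9% | 97% |
| 80% | 51 (44) | 35.2 | 99% | 47% |

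With q = 90%, P(CR given normal) = 0.87 × 0.90 / (0.87 × 0.90 + 0.13 × 0.90) = 0.783 / 0.900 = 0.87, the base rate.

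**No baseline condition.** A result of 24 normal among 27 CR participants fits anything from all 24 having been elevated and normalised to none. If the 24 were never elevated and the other 3 stayed elevated, normalisation is 0 of 3. The hypothesis as written cannot tell these apart.

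**What a CR versus non-CR contrast could deliver.** With all 4 non-CR participants sampled (27 v 4), a two-sided Fisher test at 0.05 would call the 90%/90% marker associated in 1.5% of trials. It would have 69% power if 90% of CR and 30% of non-CR participants were normal. With 44 v 7 these are 2.2% and 92%.

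The cited study suggests fewer evaluable participants. Its 62 patients were 54 CR, 6 induction deaths and 2 resistant. Scaled by 31/62, that is 27, 3 and 1. Those who die in induction give no post-therapy sample, leaving about 27 v 1. One participant gives an exact 95% interval of 0% to 97.5% or 2.5% to 100%. Fisher's test then reaches 0.05 only if all 27 CR participants are normal and the one non-CR participant is not (p = 1/28 = 0.036). At 90% and 30% normal the power is 0.9²⁷ × 0.7 = 0.058 × 0.7 = 4%. At N = 51 the resistant group is 2 × 51/62 = 1.6.

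**The case against.** The strongest reply is that the study is not confined to CR participants. Aim 1.2 names response and disease-free survival, Section 2.4.3 plans to correlate marker changes with viral load and clinical outcome, and change over time is already an aim. Plasma is scheduled regardless of response, including at early discontinuation (Section 8.4: "Plasma samples to be taken for and cytokine studies"). All of that is true. What remains is that no analysis is attached to those intentions, and the one test that is written does not serve them.

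A reader might infer that the plan would confirm an uninformative marker. The documents do not support that. It depends on most participants normalising, the 90% is assumed, and at 80% the chance that at least 80% of 27 CR participants are normal is only 54%. The base-rate result also follows by construction from equal rates. The supportable word is could.

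A reader might also infer that Aim 1.1 attributes the elevation to HL. It does not: it asks about levels in people with HL, and the rationale openly names HIV and EBV as contributors. The limit is on interpretation.

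Finally, the non-CR group may be close to empty, which stands as a limit on the remedy. Early discontinuers may add some participants, but they are sampled within 1 month, not at 6-8 weeks. After progression only survival follow-up is required (Section 8.3). Participants who finish therapy in PR would be sampled on schedule; the cited study's counts leave none (54 + 6 + 2 = 62).

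**Conclusion.** The concern holds in a limited form. The only stated test, in both appendices, has no baseline-elevated condition and no non-CR contrast. It could be satisfied without any normalisation, or by a marker unrelated to response, and so cannot by itself support objective 1.2.13. Aim 1.2 names the right outcomes without an analysis, and elevation under Aim 1.1 is not specific to HL without an HIV-positive, HL-negative comparator.

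The figures rest on an 87% CR rate borrowed from another regimen, assumed normalisation of 80% to 90%, assumed pass rules, and N of 31 or 51. The logical gap needs none of these. The 31 is itself uncertain: 20 French participants are an expectation, and footnote V conflicts with the LYSARC protocol.

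The aim is an exploratory pilot that depends on funding (Section 10.0). The primary endpoint is unaffected.

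**What to change.** Amend Appendix X, section 5.0 and Appendix XIV, section 5.0 together:

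1. Define the normal range for each marker and its reference population.
2. Restrict the normalisation analysis to participants above that range at baseline, and report paired within-participant change from baseline.
3. Report normalisation in CR and non-CR participants side by side with an exact confidence interval, labelled exploratory. State that evaluable non-CR participants may be very few, that induction deaths give no post-therapy sample, and that early discontinuers are sampled at a different time.
4. State that, without an HIV-positive, HL-negative comparator, elevation under Aim 1.1 is not specific to HL.
5. State the analysed N and reconcile Appendix I, footnote V, with section 16.1 of the LYSARC protocol.

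The cost is a paragraph in each appendix. No new sampling times are needed, and the assays are planned in batch at the end of the study, so the analysis can be written before results exist. The downside is a very wide CR versus non-CR interval, which must be reported as such.

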6.0 SHIPPING INSTRUCTIONS AND SAMPLE PROCESSING

A. General

To ship blood specimens, use a diagnostic shipper approved for a volume of at least 30 cc. The use of the SAF-T-PAK STP 210 diagnostic cardboard shipper is recommended. These shippers may be ordered at the SAF-T-PAK website www.saftpak.com. The following instructions below are for use with the recommended STP-210 shipper. If using another federally approved diagnostic shipper, please follow instructions provided for that specific shipper.

NOTE: Specimens MUST BE SHIPPED Monday through Thursday as an OVERNIGHT PRIORITY shipment. Specimens are NOT ACCEPTED ON SATURDAYS or SUNDAYS in the AMC BIOREPOSITORY.

Should the site collect specimens on Friday and Saturday, samples should be processed for plasma according to the AMC Biorepository's SOP on Separation of Plasma and Mononuclear Cells, available on the AMC Operations web site. At least four 0.5 mL aliquots of plasma are required. Aliquots should be frozen at specimens at -80°C and shipped on dry ice to the AMC Biorepository the following week.

B. Specimen preparation, packaging, and shipment

Draw two 6 cc (mL) lavender top [EDTA] tubes from study participant. Seal the tops of the tubes with parafilm. Place the two sealed tubes into bubble wrap (provided in STP-210

kit). Tape around the bubble wrap so that the roll stays together and the tubes cannot fall out or break. Place absorbent material sheet around the bubble wrapped tubes and slip into a biohazard poly-bag and "self-seal." Place poly-bag containing tubes into the white TYVEK bag and seal. Place the TYVEK bag into the STP-210 diagnostic cardboard shipper. Seal the cardboard shipper with clear packing/shipping tape.

Affix the FED-EX airbill on blank side of the shipper making sure that it is marked "FED-EX PRIORITY OVERNIGHT." Mark "OTHER" in the airbill under "Packaging." Under airbill section "Special Handling," indicate "YES-SHIPPERS DECLARATION NOT REQUIRED." Place "From/To" information onto areas provided on the shipper.

Blood specimens should be shipped by overnight express at room temperature to:

[name] George Washington University Medical Center [name] [contact] [contact] Email: [contact] [contact]

Specimen Labeling

Each sample tube should be labeled using a fine-tipped Sharpie pen with the following information:

- Protocol #: AMC-085
- 9-digit Participant ID #
- Visit #
- Date and time of specimen collection
- Specimen Type: "Plasma"
- Purpose: "Cytokine Assays"

Make certain that shipper is already either pre-labeled with 'UN#3373' stamp. Make certain that the net volume of the specimen being shipped is written in the space provided on the shipper or make a separate label with the volume in mL and affix to the shipper. Affix airbill to shipper so that the 'UN' and 'VOLUME' labels are visible. RETAIN THE TOP COPY OF THE AIRWAY BILL FOR YOUR RECORDS. Place the box in the FedEx pickup area at your site or call to request a package pickup.

Billing

Bill the FedEx number provided on the AMC members' only website. This number is supplied by the AMC Operations and Data Management Center. It is only to be used for billing shipment of specimens to the lab where the sample is processed and/or stored.

Contact for Site Questions (9AM-5PM Pacific Time) Lab Manager: [name] ([contact]) Lab [contact] [name]'s office [contact]

7.0 AMC BIOREPOSITORY INSTRUCTIONS ONLY

The AMC Biorepository will separate plasma, aliquot the plasma into as many 1.0 mL aliquots until the sample is used as per AMC Biorepository SOPs, and store at -80°C. Specimens should be sent in batch at the end of the study to:

[name] BSRB 173 UCLA AIDS Institute [name] [contact] [contact] Email: [contact]

